4.3 Test Foods

There will be two test foods:

1. Control Cookie
2. Cookie with added Fibersym

The difference in the cookies is the presence of the Fibersym, meals will therefore be matched for available carbohydrate. Both test meals will be consumed with 250ml of water.

During the 3-day pre-feeding period, subject will consume 9 cookies per day with the aim to provide approximately 29g of fibre per day from the Fibersym cookies. For the test breakfasts, the subject will consume approximately 3 cookies containing 50g available carbohydrate. The Fibersym cookies will

deliver approximately 10g of fibre. Once the cookies are baked they will be sent out for macronutrient analysis and the final weight of the cookies fed will be adjusted accordingly.

Table 1: Approximate composition of the test meals*

	Approx. # cookies	Weight (g)	Protein (g)	Fat (g)	Total carbohydrate (g)	Dietary Fibre (g)	Available carbohydrate (g)
Control Cookie	3	90	3.4	10.5	50.2	0.2	50
Fibersym cookie	3	100	3.4	10.5	60.2	10.2	50

* Once the cookies are baked they will be sent out for macronutrient analysis and the final weight of the cookies fed will be adjusted accordingly.

4.4 Standard Evening meal

All subjects will be asked to consume a standard evening meal which will be provided by GI Labs and consist of a frozen dinner, eg Stouffers Teriyaki Chicken bowl

4.5 GI Tolerability

GI tolerability will be assessed using a Physical Comfort Questionnaire (Appendix 2). Subjects will be asked to complete the Questionnaire before they start consuming the test food and every day during the 3 day pre-feeding period. During the test day, they will fill it out before consuming the test breakfast at 0min and again at 2h.

Participants mark either “yes” or “no” after each marker of physical comfort. If they mark “yes” they are instructed to rate the severity of the side-effect on a 100 mm VAS and to provide any comments they feel are necessary. The physical comfort scale includes bloating, belching, diarrhea, flatulence, nausea, headache, and a category for “other”. In the “other” category, participants will be asked to specify what they mean by “other” and rate the severity using the 100 mm line.

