2.2 Secondary objectives

- To compare the 2hour postprandial insulin incremental area under the curve (IAUC) after the Fibersym containing carbohydrate load with the control meal
- To compare the individual postprandial glucose and insulin responses at each time point after the Fibersym containing carbohydrate load with the control meal
- To compare the GI symptoms after the three days of pre-feeding of Fibersym cookies with the control meal
- To compare the satiety scores after the Fibersym containing carbohydrate load with the control meal
- SAFETY: GI symptoms and Adverse events.

3. Subject Selection

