4.2 Study Flow Chart

Visits Procedures	Screening	TEST VISITS				
	V1	3 day prefeeding	V2 Test meal	7 day wash out	3 day prefeeding	V3 Test meal
Informed Consent Process and Informed Consent Form Signature	X					
Subject's demographic data	X					
Inclusion and exclusion criteria	X					
Subject's eligibility	X					
Anthropometry	X		X			X
Check of dietary compliance		X	X		X	X
Record of supplement consumption		X			X	
Check of concomitant medications	X		X			X
2 Fasting blood samples			X			X
Consumption of test food			X			X
Postprandial blood samples 15, 30, 45, 60, 90 and 120min after starting to eat		X	X		X	X
GI Symptom Questionnaire		X	X		X	X
Satiety Questionnaire			X			X
Check of adverse events	X		X		X	X

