4.6 Satiety

Subjective measurements of palatability, motivation to eat and physical comfort will be assessed using visual analog scales (VAS) (Appendix 3) at the same time points blood samples are collected. Each of the questions on the VAS is a 100 mm line anchored at each end with opposing statements (Rogers and Blundell 1979). For instance, fullness is assessed with the following statement on the left side of the line “not full at all” with the following statement to the right side of the line “As full as I

have ever felt". Participants make a vertical mark on the line at a point that they feel reflects their feelings at the moment the test was taken. Scores will be assessed by measuring the distance between the intersection of the mark on the line and the left end of the line (see Appendix 3).

The Motivation to Eat questionnaire includes 4 questions:

Q1: How strong is your desire to eat? ("very weak" to "very strong")

Q2: How hungry do you feel? ("not hungry at all" to "as hungry as I have ever felt")

Q3: How full do you feel? ("not full at all" to "as full as I have ever felt")

Q4: How much do you think you could eat now? ("nothing at all" to "a large amount")

Average appetite score is calculated as a summary measure using the following equation:

$$\text{Average appetite} = [Q1 + Q2 + Q4 + (100 - Q3)] / 4$$

Since Question 3 assesses fullness, it has opposite anchors at each end of the 100 mm line compared to the other 3 questions. Therefore, Q3 is subtracted from 100 in the equation to adjust for this difference.

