5.1 Calculations

The incremental areas under the blood glucose and serum insulin response curves (iAUC), ignoring area below fasting, will be calculated using the trapezoid rule (Wolever et al, 1986, 2004). Fasting glucose and insulin will be taken to be the mean of the concentrations in the 2 fasting samples.

GI symptoms and Satiety calculations – to be added

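### The GI symptom form in Appendix 2 does not match section 4.5 (no headache row and, as extracted, no yes/no field), so a blank line cannot separate no symptom from a skipped item

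*Combined protocol and SAP*

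**What the plan says.** Section 2.2 includes the objective "To compare the GI symptoms after the three days of pre-feeding of Fibersym cookies with the control meal" and lists GI symptoms again under safety.

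Section 4.5 names the Physical Comfort Questionnaire in Appendix 2 as the instrument. A yes or no is marked "after each marker of physical comfort", and only after a yes is severity recorded: "they are instructed to rate the severity of the side-effect on a 100 mm VAS". The items are "bloating, belching, diarrhea, flatulence, nausea, headache, and a category for" other symptoms. The form is completed "before they start consuming the test food and every day during the 3 day pre-feeding period", and on the test day at 0 min and 2 h. The section 4.2 flow chart has a matching row, "GI Symptom Questionnaire", at pre-feeding and at both test visits.

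Appendix 2, as extracted, has three column headings (symptoms, severity, comment) and six rows: bloating, belching, nausea, diarrhea, flatulence and other. Each severity line runs from low to high.

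Section 4.6 says, after mentioning palatability, "motivation to eat and physical comfort will be assessed using visual analog scales (VAS) (Appendix 3", and ties these ratings to the blood-sample times. Appendix 3 contains only hunger, fullness, desire to eat and prospective consumption.

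Section 5.1 leaves "GI symptoms and Satiety calculations" to be added. Section 5.2 gives no rule for blank or missing answers.

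**The concern.** Section 4.5 describes a gated item: the yes/no mark records whether the symptom occurred, and the line records how bad it was. Under that design a blank line is the expected record of no, and the yes/no mark is what shows that the item was answered. If the printed form has no place for that mark, the same blank also results when a subject overlooks the item. The low-to-high anchors suit a line used only after a yes and are not themselves a departure from section 4.5. They do mean that no point on the line stands for absence, so a symptom-free subject has no obvious way to record that on the line.

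Incidence and mean severity of GI symptoms both depend on how blanks are read. A scoring rule can assign a value to a blank but cannot establish what the subject meant, so the gap is best closed before any form is filled in. Separately, headache is meant to be prompted, but on the printed form it appears only if the subject volunteers it under the other category. Section 4.6 adds a third mismatch, because it points physical comfort to a form and a timetable that do not carry it.

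**Working it through.** The plan states no figure to reproduce here. The check sets the sections side by side, then illustrates the size.

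**Items.** Section 4.5 lists six named symptoms plus other, 7 items. Appendix 2 has five named symptoms plus other, 6 rows. 7 − 6 = 1, and the missing item is headache. The other row labels were extracted intact, so this part is firm.

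**Yes/no field.** Section 4.5 requires one per item. Appendix 2 shows none in its headings or rows. An unlabelled tick-box could have been lost in PDF reading, so this part is probable rather than certain.

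**Physical comfort.** Section 4.6 gives Appendix 3 at every blood-sample time. Section 4.5 gives Appendix 2, at 0 min and 2 h on the test day. Section 4.1 also puts the GI questionnaire at fasting and 2 h, and Appendix 3 has no physical comfort item. Section 4.6 is therefore out of line with the other three places.

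**Forms exposed.** Per food: 3 daily + 2 on the test day = 5, or 6 if the form before starting is separate. Over 2 foods and 15 subjects: 5 × 2 × 15 = 150 to 6 × 2 × 15 = 180 forms. This counts forms in use, not errors.

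**Size for one symptom.** The 15 subjects come from section 3.1. Everything else is assumed: 10 of 15 symptomatic on Fibersym, 2 of 15 on control, severity s = 30 mm whenever present, no written as 0 mm, and m symptomatic Fibersym subjects skipping the line.

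- Control mean: 2 × 30 / 15 = 4 mm.
- Skips read as no: difference = (10 − m) × 30 / 15 − 4.
- Skips treated as missing: difference = (10 − m) × 30 / (15 − m) − 4.

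| m | Read as no | Treated as missing | Error |
|---|---|---|---|
| 1 | 9 × 30 / 15 − 4 = 14 mm | 9 × 30 / 14 − 4 = 15.3 mm | 1.3 mm |
| 2 | 8 × 30 / 15 − 4 = 12 mm | 8 × 30 / 13 − 4 = 14.5 mm | 2.5 mm |

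With m = 0 the two codings coincide and the error is zero. The error is proportional to s. At 20 mm and one skip it is 1.29 × 20 / 30 = 0.9 mm; at 50 mm and two skips it is 2.46 × 50 / 30 = 4.1 mm. These are differences of the two food means. A complete-pairs analysis would shift them somewhat, depending on whether the subjects who skipped also had the symptom on control.

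**The case against.** Several points on the other side stand, and they limit the size of the problem.

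- The instruction to mark yes or no is in section 4.5 whatever the form looks like, and subjects could write it in the comment column. Section 5.2 refers to a query process that could chase blanks, although recall will limit it for symptoms over several days.
- Section 7.4 counts any symptom as an adverse event and has events assessed at each visit, so a headache has another route into the record. Headache is also not a GI symptom. That route does not supply a per-symptom 0 to 100 mm score.
- The synopsis omits GI symptoms from its secondary outcomes and gives only adverse events under safety. Section 2.2 does list GI symptoms under both, so the objective exists, but its standing is not uniform across the document.
- Section 5.1 says the GI calculations are to be added, not that they will be added after collection.

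A reader might infer something much larger: that the form could move the estimated difference from 0 mm to 16 mm. In the example above, dropping every blank gives 30 − 30 = 0 mm, while scoring blanks as zero with nobody skipping gives 10 × 30 / 15 − 4 = 16 mm. The documents do not support blaming the form for that. The same gap would appear with perfect yes/no boxes, depending on whether severity is averaged over symptomatic subjects only or over everyone. It reflects the summary left open in section 5.1. The form's own contribution is confined to skipped items being read as no.

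**Conclusion.** The inconsistency holds. The missing headache row is certain on the text, the missing yes/no field is probable, and the reference in section 4.6 to physical comfort on Appendix 3 cannot stand beside section 4.5. The consequence is an ambiguous blank on a secondary and safety outcome, with the glucose IAUC comparison unaffected. Queries and adverse event recording mitigate this only in part.

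The likely effect is small: about 1.3 to 2.5 mm on a 100 mm scale for one or two skipped lines. That rests on the assumed 10/15 and 2/15 incidences, 30 mm severity, and skips occurring only among symptomatic Fibersym subjects, in which case the Fibersym excess is understated. Skips by symptom-free subjects would do no harm when read as no, and skips among symptomatic control subjects would push the difference the other way. The category is internal inconsistency and the severity is low. The reason to act is that the fix is cheap and the lost information cannot be reliably recovered afterwards.

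**What to change.** Before data collection:

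1. Look at the source form to confirm whether yes/no boxes are present.
2. If they are absent, add a yes and a no box to each item in Appendix 2. Add a headache row in either case, so that the form matches section 4.5.
3. Reconcile the physical comfort wording in section 4.6 with section 4.5 and Appendix 3, so that one instrument and one set of times is stated.
4. In section 5.1, state that no is scored 0 mm and that an item with neither box marked is missing. State also that the foods are compared within subject for incidence and for severity with zeros included. Taking incidence from the box keeps a yes marked at the far left of the line distinct from a no.

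The cost is one form revision and a few sentences in sections 4.6 and 5.1.

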4.6 Satiety

Subjective measurements of palatability, motivation to eat and physical comfort will be assessed using visual analog scales (VAS) (Appendix 3) at the same time points blood samples are collected. Each of the questions on the VAS is a 100 mm line anchored at each end with opposing statements (Rogers and Blundell 1979). For instance, fullness is assessed with the following statement on the left side of the line “not full at all” with the following statement to the right side of the line “As full as I

have ever felt". Participants make a vertical mark on the line at a point that they feel reflects their feelings at the moment the test was taken. Scores will be assessed by measuring the distance between the intersection of the mark on the line and the left end of the line (see Appendix 3).

The Motivation to Eat questionnaire includes 4 questions:

Q1: How strong is your desire to eat? ("very weak" to "very strong")

Q2: How hungry do you feel? ("not hungry at all" to "as hungry as I have ever felt")

Q3: How full do you feel? ("not full at all" to "as full as I have ever felt")

Q4: How much do you think you could eat now? ("nothing at all" to "a large amount")

Average appetite score is calculated as a summary measure using the following equation:

$$\text{Average appetite} = [Q1 + Q2 + Q4 + (100 - Q3)] / 4$$

Since Question 3 assesses fullness, it has opposite anchors at each end of the 100 mm line compared to the other 3 questions. Therefore, Q3 is subtracted from 100 in the equation to adjust for this difference.

4.7 Randomization

Eligible subjects will be randomized using an online randomization calculator. Orders will be assigned to subjects in the order they attend the first visit after being recruited.

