CRITERIA FOR EVALUATION:	
EFFICACY: Primary outcome is comparison of the glucose IAUC of the Fibersym meal with the control meal.
 
Secondary outcomes: comparison of the insulin (IAUC) of the Fibersym meal with the control meal, comparison of glucose and insulin levels at each time point and satiety scores at each time point.
 
SAFETY: Adverse events.

STATISTICAL METHODS:	Results for all foods in a series will be compared by GLM ANOVA. After demonstrating significant heterogeneity, the significance of the differences will be tested using Tukey method to adjust for multiple comparisons
Ethics Board Approval	The investigator will be responsible for submission of the study to the Western Institutional Research Board. Prior to submission of the application, the sponsors and all co-investigators will be given the opportunity to review the application. Submission of the application will only take place if all parties agree. The Western Institutional Review Board® meets all requirements of the US Food and Drug Administration (FDA), the Department of Health and Human Services (DHHS), the Canadian Health Protection Branch (HPB), Canadian Institutes of Health Research (CIHR) and the European Community Guidelines. Participants will not be enrolled into the study until they have had the study procedures explained to them, had a chance to ask questions, and given their voluntary consent by signing the consent form. Participants who do not understand English will not be enrolled.
Subject Selection Criteria	
Inclusion criteria:
 
 1. Male or non-pregnant females, 18-75 years of age, inclusive 2. Body mass index (BMI) between 18.5 and 35 kg/m² inclusive at screening. 3. Systolic blood pressure < 130mmHg, Diastolic Blood pressure <90mmHg. 4. Willing to maintain habitual diet, physical activity pattern, and body weight throughout the trial. 5. Subject is willing to abstain from strenuous exercise, or consume alcoholic drinks 24hours before study days. 6. Absence of health conditions that would prevent fulfillment of study requirements as judged by the Investigator on the basis

of medical history.

7. Understanding the study procedures and willing to provide informed consent to participate in the study and authorization to release relevant protected health information to the study investigator.
8. Female subjects are willing to use a contraceptive method to avoid pregnancy during the study period.

Exclusion criteria:

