2.1 Primary objective

- To compare the 2 hour postprandial glucose incremental area under the curve (IAUC) after the Fibersym containing carbohydrate load with the control meal

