3.1 Type and number of subjects

Fifteen (15) healthy adult males or non-pregnant females recruited from the pool of subjects who have previously participated in studies at GI Labs and have given permission to be contacted to be recruited for future studies or using online advertising and/or posters. Each subject will have to fulfill all inclusion criteria and will not be allowed to meet any of the exclusion criteria.

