3.4 Withdrawal Criteria

- Withdrawal of consent for any reason
- During the course of the study, the development of an injury or illness or initiation of use of a medication which, in the opinion of [name], makes the subject's continued participation dangerous to the subject or to others, or which may affect the results.
- Failure to follow GI Labs safety guidelines
- Repeated failure to attend at scheduled visits
- Repeated failure to follow the protocol

4. Study Design and Procedures

The study is double-blind with a randomized, cross-over design.

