5.2 Statistical Analysis

No interim analyses are planned. All summaries of demographics, baseline characteristics, efficacy and safety will be performed after all subjects complete both periods and the data collection and query processes are finalized.

Descriptive Statistics: All continuous data will be summarized by number of subjects assessed, mean, standard deviation (SD), median and range (minimum and maximum values). Demographic and baseline characteristics to be summarized include gender; ethnicity; height (m); weight (kg); body mass index (BMI) (kg/m²) and blood pressure (mmHg).

Data will be analyzed using General Linear Model analysis of variance (GLMANOVA). After demonstration of significant heterogeneity, the individual means will be compared using Tukey's test to adjust for multiple comparisons. The criterion for statistical significance will be a 2-tailed $p<0.05$.

6. Study Product

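### The two-period crossover in 15 subjects states neither a balance rule for the two orders nor a period term in the model; adding both is a cheap improvement

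*Combined protocol and SAP*

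**What the plan says.** Section 4 describes the design: "The study is double-blind with a randomized, cross-over design". Section 4.3 lists two foods, and sections 4.1 and 4.2 give two test visits, V2 and V3, so only two orders exist. Section 3.1 sets the size: "Fifteen (15) healthy adult males or non-pregnant females".

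On how the orders are allocated, section 4.7 says "Eligible subjects will be randomized using an online randomization calculator. Orders will be assigned to subjects in the order they attend the first visit after" recruitment. Section 4.1 repeats the calculator. Neither section gives an order ratio, a block size or any rule that the two orders be used about equally.

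On the analysis, section 5.2 says "Data will be analyzed using General Linear Model analysis of variance (GLMANOVA"), followed by Tukey's test. The synopsis, under Statistical Methods, says "Results for all foods in a series will be compared by GLM ANOVA". Food is the only factor named. Period, sequence and subject are not mentioned as model terms. Section 5.2 does acknowledge the period structure when it places the summaries "after all subjects complete both periods".

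**The concern.** In a two-period crossover, the two visits can differ for reasons unrelated to the food. Here they may be up to 4 weeks apart, the second follows a second course of pre-feeding, and section 4.10 allows either of two glucose analysers and notes that the method may change. If the orders are unequal and period is not fitted, part of such a shift enters the food difference for glucose IAUC, the primary outcome, and for every secondary comparison. If the orders are nearly equal, the shift hardly moves the estimate, but it adds to the error term and widens the interval.

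The plan can be followed to the letter with a lopsided split and no period term, or the model can be settled after the data are seen. The trial has 15 subjects and states no power calculation, so precision should not be given away.

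The point at which an order is assigned is also unclear. The visit meant in section 4.7 cannot be V2, because product-specific cookies are eaten for 3 days before it. If it is V1, eligibility is still being determined there (section 4.1), and a screening failure could use up an order.

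**Working it through.** **Inputs from the documents.** N = 15 (section 3.1); two foods, two periods; two-sided 0.05 (section 5.2). The plan has no figure to reproduce: it gives no power, effect size, SD, dropout rate or period effect.

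**Assumptions.** A within-subject analysis (paired differences), which the plan does not spell out. Simple 1:1 randomisation where probabilities of a split are given. A shift π = V3 minus V2 of 0 to 1 SD of the within-subject food difference.

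**Step 1: share of the shift in the unadjusted estimate.** Let n1 subjects receive control first and n2 Fibersym first. Their Fibersym-minus-control differences have means τ + π and τ − π, where τ is the true food effect. The overall mean is τ + π(n1 − n2)/15. At 8:7 the share is 1/15 = 6.7%; at 10:5, 5/15 = 33%; at 11:4, 7/15 = 47%. With 15 completers it cannot be zero.

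**Step 2: how likely each split is.** For 10:5 or worse, 2 × (3003 + 1365 + 455 + 105 + 15 + 1)/2^15 = 9888/32768 = 0.302. For 11:4 or worse, 2 × 1941/32768 = 0.118. Exactly 8:7 has probability 0.393.

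**Step 3: type I error without period, given the split** (100,000 simulated trials per case). The last column is the variance factor if period is fitted, 15(1/n1 + 1/n2)/4.

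| Split | Share | π = 0.25 SD | π = 0.5 SD | π = 1 SD | Variance factor with period |
|---|---|---|---|---|---|
| 8:7 | 6.7% | 0.044 | 0.030 | 0.007 | 1.004 |
| 10:5 | 33% | 0.054 | 0.061 | 0.068 | 1.125 |
| 11:4 | 47% | 0.064 | 0.099 | 0.169 | 1.278 |
| 12:3 | 60% | 0.079 | 0.154 | 0.355 | 1.563 |

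With period fitted, type I error is about 0.05 in every row.

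**Step 4: averaged over simple randomisation.** The expected value of (n1 − n2)/15 is zero, so expected bias is zero, and simulated type I error without period is 0.049 to 0.051. The SD of the estimate is sqrt((1 + π²)/15): 0.258 at π = 0 and 0.289 at π = 0.5. For a true effect of 0.778 SD, chosen because it gives a paired test 80% power at n = 15, simulated power is:

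| Orders and model | π = 0 | 0.25 | 0.5 | 1 |
|---|---|---|---|---|
| Simple, no period | 0.80 | 0.78 | 0.71 | 0.50 |
| Simple, period fitted | 0.77 | 0.77 | 0.76 | 0.77 |
| 8:7, no period | 0.80 | 0.80 | 0.76 | 0.58 |
| 8:7, period fitted | 0.80 | 0.79 | 0.79 | 0.80 |

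**Step 5: 95% half-width at 8:7, in SD units.** Without period, the ±π values add a sample variance of π²(15 − 1/15)/14 = 1.067π². The half-width is 2.145 × sqrt((1 + 1.067π²)/15), on 14 df:
- π = 0: 0.554
- π = 0.25: 0.572
- π = 0.5: 0.623
- π = 1: 0.796

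With period, it is 2.160 × 0.5 × sqrt(1/8 + 1/7) = 2.160 × 0.2588 = 0.559, on 13 df, whatever π is.

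**The case against.** Three stronger readings are tempting, and the documents support none of them.

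- **The randomisation is unrestricted.** A reader might infer this, but sections 4.1 and 4.7 are silent on restriction. An online calculator can produce a blocked list, and assignment in order of attendance fits a list prepared beforehand.
- **Period is excluded from the model.** A reader might infer this from the naming of foods alone. Section 5.2 gives no list of terms at all. Subject is not named either, yet a crossover analysis would be expected to use it, so silence cannot be read as including one and excluding the other.
- **The primary result is systematically biased.** Only the fraction |n1 − n2|/15 of a shift enters. Over repeated simple randomisations it averages to zero and type I error holds. At 8:7 the unadjusted test is conservative, not liberal.

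It can also be said that a large shift is unlikely. Section 4.1 standardises the evening meal, the fast, alcohol and activity, and reschedules subjects who are unwell or non-compliant. Section 3.1 draws partly on people who have already taken part in studies at the site. A shift of 1 SD would exceed the food effect of 0.778 SD used above. With no shift, fitting period gains nothing: the half-width goes from 0.554 to 0.559 SD.

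All of this stands. What remains is that neither safeguard is written down, and that the split actually drawn matters for this one trial even when the average over splits does not. An odd number of subjects is not itself a fault: once period is fitted, 8:7 costs 0.4% in variance.

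**Conclusion.** The point holds as a cheap improvement, not as a demonstrated flaw. The plan does not state how the two orders are balanced or whether period is in the model. If period is left out, the harm is split-dependent distortion plus lost precision.

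The size rests on a period shift that the documents do not give. At 8:7, omitting period makes little difference up to an assumed 0.25 SD (half-width 0.57 against 0.56 SD). At 0.5 SD it widens the interval by about 11% (0.623/0.559), and at 1 SD by about 42% (0.796/0.559). At 11:4, which has probability 0.12 or less under simple 1:1 randomisation, an assumed 0.5 SD shift would give a type I error of about 0.10.

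The two parts of the remedy work together. Fitting period alone under simple randomisation leaves power at about 0.76 to 0.77 in the example; holding the orders to 8:7 as well brings it to about 0.79 to 0.80.

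**What to change.** In section 4.7, state that the order list is generated in advance with the two orders restricted to 8 and 7. Blocks of 2 or 4 achieve this for 15 subjects. Blocks of 6 do not guarantee it, since the last three subjects could all receive the same order and give 9:6. State also that an order is assigned only after eligibility is confirmed and before any pre-feeding cookies are dispensed.

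In section 5.2 and the synopsis, state that the model for glucose IAUC contains subject, period and food, and that the period-adjusted food difference is reported with its 95% confidence interval. The same model can serve the insulin IAUC and the other continuous secondary outcomes. If withdrawals change the split (to 7:7 or 8:6, say), the adjusted estimate remains free of the shift.

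The cost is a few sentences and one error degree of freedom (14 to 13; critical t 2.145 to 2.160). If there is no period shift, the interval is about 1% wider (0.554 to 0.559 SD). No extra subjects or visits are needed.
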